2.8.4 Other safety data

2.8.4.1 ECG and cardiac imaging data

ECGs are scheduled at screening, Day 1 (pre-dose and 4 hours post dose), Day 2, Day 4, Day 6 (if required in the opinion of the investigator) and at Day 10 (if required in the opinion of the investigator). In case of safety concerns, additional ECGs must be performed to confirm the safety. A copy of the local tracing will be sent to a central ECG reader.

Only “QTcF interval, aggregate” will be recorded on the local ECG crf page. The interpretation of the ECG (normal, abnormal) will also be collected on the local ECG crf page.

2.8.4.1.1 Clinically significant changes in ECG parameters

The number and percentage of participants meeting the Fridericia QTcF interval criteria defined below at any time post-baseline will be summarized by treatment group (new means that the criteria were not met at baseline or was missing at baseline):

Fridericia QTc interval: new > 480 msec, new > 500 msec, change from baseline 30 - 60 msec, change from baseline > 60 msec, New > 500 msec and change from baseline > 60 msec

Summary of clinically significant changes in ECG will be based on ECG recorded locally .

2.8.4.1.2 Overall interpretation of the ECGs – ECG findings

Recording of ECG findings (e.g. prolonged QTc, Torsade de Pointes, Ventricular Tachycardia,..) will be send to Novartis by the central ECG vendor.

ECG findings will be summarized by treatment group and visit/time-points.

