6.1.3 Treatment duration

The total treatment duration of hydroxychloroquine is 10 days. The approach to include a loading dose on Day 1 is preferred in order to rapidly reach higher target tissue drug concentrations. The total treatment duration of azithromycin will be 5 days.

In case a participant is discharged prior to Day 10, they may complete study treatment as planned, at home, until Day 10 if QTcF \leq 480 ms at the time of discharge based on the local ECG data. Otherwise, treatment will be discontinued at the time of discharge.

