12.5.1 Safety endpoints

For all safety analyses, the safety set will be used. All listings and tables will be presented by treatment group.

Safety summaries (tables, figures) include only data from the on-treatment period with the exception of baseline data which will also be summarized where appropriate (e.g. change from baseline summaries). In addition, a separate summary for death including on treatment and post treatment deaths will be provided. In particular, summary tables for adverse events (AEs) will summarize only on-treatment events, with a start date during the on-treatment period (treatment-emergent AEs).

The on-treatment period lasts from the date of first administration of study treatment to 30 days after the date of the last actual administration of any study treatment.

Adverse events

A treatment-emergent AE is defined as any AE that develops after initiation of the study treatments or any event already present that worsens following exposure to the study treatment.

All information obtained on adverse events will be displayed by treatment group and participant.

The number (and percentage) of participants with treatment-emergent adverse events (events started after the first dose of study medication or events present prior to start of double-blind treatment but increased in severity based on preferred term) will be summarized in the following ways:

- by treatment, primary system organ class and preferred term.
- by treatment, primary system organ class, preferred term and maximum severity.
- by treatment, Standardized MedDRA Query (SMQ) and preferred term.

Separate summaries will be provided for study medication related adverse events, death, serious adverse events, other significant adverse events leading to discontinuation.

A participant with multiple adverse events within a primary system organ class is only counted once towards the total of the primary system organ class.

Vital signs

All vital signs data will be listed by treatment group, participant, and visit/time and if ranges are available, abnormalities will be flagged. Summary statistics will be provided by treatment group and visit/time.

ECG

The overall interpretation of the ECGs will be summarized by treatment group and visit/time.

Any clinically significant changes in ECG parameters will be summarized by treatment group.

Summary statistics will be presented by treatment and visit/time, as appropriate.

Clinical laboratory evaluations

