2.1.1.7 By-visit summary

By-visit summary will be provided for the following safety endpoints: ECG, vital signs and Lab (Hemathology, Chemistry, Inflammatory markers). *Nominal visits* (i.e. the scheduled visits collected in the database) will be used to summarize these endpoints.

For efficacy endpoints: the score achieved on the 9-item ordinal scale by Day 15 or by Day 28 will be reported. Accordingly, nominal visits will not be used. For this analysis, in case more than one assessment were performed on the same day, schedule assessment will be preferentially used.

Viral clearance will be reported by Day 6 and by Day 10; nominal visits will not be used to summarize these endpoint.

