2.1.1.7.1 Rule for re-mapping visits which are not time-point specific

The early discharge visit and unplanned assessments, which are not time point specific, will be remapped to one of the scheduled time-point based on rules provided in [Table 2-1](#), [Table 2-2](#) and [Table 2-3](#). The remapped visit will only be used in analysis, in case the corresponding schedule visit is missing.

Table 2-1 Remapping rule for vital signs

Visit	Visit window (study days)	Target Day
Baseline*	See Section 2.1.1.3	
Day 1	1	1
Day 2	2, 3	2
Day 4	4, 5	4
Day 6	6, 7	6
Day 8	8, 9	8
Day 10	10,11	10
Day 40	12 to 40	40

* Note: A screening assessment performed on study day 1, will be mapped to the baseline visit.

Table 2-2 Remapping rule for Lab (Hemathology, Chemistry, Inflammatory markers)

Visit	Visit window (study days)	Target Day
Baseline*	See Section 2.1.1.3	
Day 1	1	1
Day 4	2 to 6	4
Day 10	7 to 12	10
Day 15	13 to 17	15
Day 40	18 to 40	40

* Note: A screening assessment performed on study day 1, will be mapped to the baseline visit.

Table 2-3 Remapping rule for ECG

Visit	Visit window (study days)	Target Day
Baseline*	See Section 2.1.1.3	
Day 1§	1	1
Day 2	2, 3	2
Day 4	4, 5	4
Day 6	6, 7	6
Day 10	8 to 12	10
Day 40	13 to 40	40

* Note: A screening assessment performed on study day 1, will be mapped to the baseline visit.

§ only applies to unplanned assessment performed on Day 1. For assessment performed at “Day 1-pre-dose” or at “Day 1 4 hours post-dose”, remapped visit (AVISIT) will be labelled “Day 1 pre-dose” or “Day 1 4 hours post-dose”.

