2.1.1.7.2 Handling of multiple assessments within visit windows

In case multiple assessments of a participant may fall in a particular window, all results will be displayed in listings, but for summary statistics, only the value closest to the actual target day will be used. If two assessments are separated by the same number of days from the target day, the earlier assessment will be used. If an unplanned or unscheduled assessment (e.g. discharge visit) were conducted on the target day but a schedule assessment for this assessment is also available, the schedule assessment will be used.

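### A central rhythm finding seen only on an unplanned or early-discharge ECG, in a window whose scheduled ECG was done, and not reported by the site as an adverse event, enters no per-arm count

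*SAP*

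**What the plan says.** SAP 2.8.4.1.2 states that the central ECG vendor supplies the findings, and plans this output: "ECG findings will be summarized by treatment group and visit/time-points". This follows Protocol 12.5.1: "The overall interpretation of the ECGs will be summarized by treatment group and visit/time".

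Three SAP rules decide which tracings reach a by-visit ECG summary:

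- 2.1.1.7 uses nominal (scheduled) visits for ECG, vital signs and laboratory summaries.
- 2.1.1.7.1: "The early discharge visit and unplanned assessments, which are not time point specific, will be remapped to one of the scheduled time-point". It then adds: "The remapped visit will only be used in analysis, in case the corresponding schedule visit is missing".
- 2.1.1.7.2, where several assessments share a window: "all results will be displayed in listings, but for summary statistics, only the value closest to the actual target day will be used".

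Unscheduled tracings are expected. SAP 2.8.4.1 says: "In case of safety concerns, additional ECGs must be performed to confirm the safety". Protocol 8.4.4 sets the number of repeats at two. Protocol 6.1.3 lets a participant go home on study drug depending on QTcF "at the time of discharge based on the local ECG data".

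The SAP has one any-time post-baseline ECG count by participant. It is in 2.8.4.1.1, covers QTcF thresholds only, and uses locally recorded ECGs.

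**The concern.** Protocol 4.5 singles out QT prolongation and pro-arrhythmia as the more relevant risk of short-term hydroxychloroquine and azithromycin. The safety endpoint in Protocol Table 2-1 is framed as a number of participants with clinically significant changes, ECG included. A by-visit table shows what was seen at each visit. It does not show how many participants per arm ever had a given finding.

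The selection rules add to this. An ECG taken outside the schedule, because something looked wrong or because the participant was leaving hospital, gives way to the scheduled ECG of the same window. If the scheduled tracing is clean and the extra one shows a run of ventricular tachycardia, the table shows the clean one. The SAP avoids this for QTcF by counting at any time, but has no matching count for rhythm findings. What could be lost is a small number of participants from a between-arm comparison on the risk the protocol regards as most relevant.

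**Working it through.** The plan states no figure on this point, so the check traces which tracings enter which output.

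**Step 1: windows.** Window limits come from SAP Table 2-3. The ECG schedule comes from SAP 2.8.4.1 and Protocol Table 8-1.

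| Window | Study days | Length | Scheduled ECG | Unplanned or early-discharge ECG in the by-visit table? |
|---|---|---|---|---|
| Day 1 | 1 | 1 | Pre-dose and 4 h | Can enter: unplanned Day 1 ECGs have their own row |
| Day 2 | 2–3 | 2 | Yes | Not if the Day 2 ECG exists |
| Day 4 | 4–5 | 2 | Yes | Not if the Day 4 ECG exists |
| Day 6 | 6–7 | 2 | Optional | Not if the Day 6 ECG was done |
| Day 10 | 8–12 | 5 | Optional | Not if the Day 10 ECG was done |
| Day 40 | 13–40 | 28 | None | Can enter; see Step 4 |

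Scheduled after Day 1: 2 + 2 = 4 days. Optional: 2 + 5 = 7 days. None scheduled: 28 days. Sum: 4 + 7 + 28 = 39, which is Days 2–40. With only the Day 2 and Day 4 ECGs done, the exclusion covers 4 days. With the optional ones as well, it covers 4 + 7 = 11 days (Days 2–12). These are window lengths, not event risks.

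**Step 2: other outputs that might count the same finding.**

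- QTcF any-time count (SAP 2.8.4.1.1): includes a participant for the QTcF value, not for a rhythm finding.
- Local ECG page (SAP 2.8.4.1): QTcF and a normal/abnormal interpretation, with no named rhythm.
- ECG measurements (SAP 2.8.4.1.3): central, but by visit and not findings.
- Adverse-event tables (SAP 2.8.1): count an arrhythmia per arm whenever it occurs after the start of treatment, but only if the site reported it.
- Disposition (SAP 2.3.1): tabulates stopping study drug by reason, not by ECG finding.

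A central finding that is on an excluded tracing and was not reported by the site is in none of these as a per-arm count.

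**Step 3: repeat tracings.** One triggering ECG plus two repeats (Protocol 8.4.4) makes 1 + 2 = 3 tracings.

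- Trigger is a scheduled ECG: that tracing and its finding are in the table, and leaving out the repeats does not lose the participant.
- Trigger is unplanned and the window's scheduled ECG exists: 0 of 3 enter.
- Trigger is unplanned and the window has no scheduled ECG: at least 1 of 3 enters; how many depends on Step 4.

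**Step 4: windows with no scheduled ECG.** The remapping rule lets the unplanned tracing in. A finding is then lost only if the closest-to-target rule of 2.1.1.7.2 also governs categorical findings. For illustration, take a finding on Day 13 and a clean unplanned ECG on Day 20. The distances to Day 40 are 40 − 13 = 27 and 40 − 20 = 20. If the rule applies, Day 20 is kept and the Day 13 finding drops out. If it does not, both can be tabulated. The rule is worded for *summary statistics*, a term the SAP also uses in the title of 2.8.4.1.3 for measurements, whereas 2.8.4.1.2 says only that findings are summarised. Either reading is possible.

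**Step 5: scale.** SAP 1.1 gives 20 randomised including one mis-randomised participant, who by the definition in SAP 2.2 was untreated. The Safety Set is therefore at most 20 − 1 = 19. Arm sizes are not given.

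**The case against.** The strongest case for the plan is that little is left uncounted. Protocol 8.4.4 requires abnormalities the site judges clinically significant to go on the CRF, as adverse events where appropriate. Protocol 10.2.1 requires treatment to stop and a cardiologist to be consulted for a documented new arrhythmia. QTcF has its own any-time count. The study was halted, reporting is descriptive, and listings for at most 19 people can be read one by one. All of this stands, and it keeps the point at the lowest level of importance. It does not close the gap for a finding the site missed, judged unimportant, or read differently from the central reader.

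A reader might also infer stronger things that the documents do not support:

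- *That the SAP departs from the protocol.* It does not; the protocol asks for the same by-visit presentation.
- *That the SAP breaks its own statement in 2.8 about including all treatment-emergent data.* That sentence describes the safety analysis as a whole, and the listings satisfy it.
- *That findings on Days 13–40 are dropped.* This holds only under one reading of 2.1.1.7.2.
- *That ECGs taken for safety concerns generally fall out of the table.* Unplanned Day 1 tracings have a row, and a scheduled ECG that prompts repeats is itself tabulated.
- *That an arrhythmia was in fact missed.* Nothing in the documents shows one.

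**Conclusion.** The point holds as a narrow gap. Three conditions must all be met: the rhythm finding is only on an unplanned or early-discharge tracing; the scheduled ECG of that window exists (Days 2–5, and Days 6–12 if the optional ECGs were done); and the site did not report an adverse event. The finding is then in listings but in no count by arm. For windows with no scheduled ECG the text leaves the matter open.

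This rests on taking the remapping rule at its word, as governing use in analysis and so covering categorical findings as well as measurements. The effect is small, and no test or decision depends on the table. It is an optional improvement, worth making because it is cheap and because it treats rhythm findings as the SAP already treats QTcF.

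**What to change.** Add to SAP 2.8.4.1.2 the number (%) of Safety Set participants per arm with each new centrally read ECG finding at any time post-baseline. Use all scheduled, unscheduled, repeat and discharge tracings, and count each participant once per finding. State that the selection rules of 2.1.1.7.1 and 2.1.1.7.2 do not apply to this count; that also removes the Days 13–40 ambiguity for it. Keep the by-visit table, footnote the number of ECGs per arm, and flag findings that repeat tracings did not confirm.

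The cost is a short SAP addition and one table, from central-reader data the sponsor already receives. Two limits should be stated with it. Participants with more ECGs have more chances of a finding. Under continuous telemetry only one time point per required ECG day goes to the central reader (Protocol 8.4.4), so the count supplements the adverse-event tables and is not a complete arrhythmia incidence.

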2.8.4.1.3 Summary statistics of ECG parameters (i.e. measurements)

Summary statistics of ECG parameters will be presented by treatment and visit/time. This analysis will be based on ECG parameters assessed centrally.

2.8.4.2 Vital signs

Vital signs measurement include: weight (kg), temperature (C), pulse rate (beats/min), systolic blood pressure (mmHg), diastolic blood pressure (mmHg), oxygen saturation (%) and respiratory rate (breaths/min).

Vital signs measurement will be analyzed using descriptive summary statistics for the change from baseline by treatment group and visit/time.

2.8.4.3 Chest imaging

In case of available records findings, chest imaging will be recorded in the CRF, at screening and at Day 15/early withdrawal.

Chest imaging (X-ray or and CT scan) data will summarized at baseline ([Section 2.3.2](#)).

2.9 Biomarkers

Analysis of other biomarkers will not be conducted.

2.10 Interim analysis

No formal interim analysis is planned for this trial.

3 Sample size calculation

3.1 Primary endpoint

Assuming a true treatment difference in clinical response of 20% for hydroxychloroquine plus azithromycin plus SoC vs. placebo plus SoC, and an odds-ratio of at least 2.25, a sample size of 148 participants per treatment group (444 overall) provides at least 93% power that the primary analysis will be statistically significant at the two-sided 5% significance level. This holds for a variety of different assumptions with respect to treatment and clinical response rates.

These sample size assumptions were evaluated using East Version 6.4.

The sensitivity of different assumptions for clinical response rate for treatment and control groups and effect size on power are summarized in [Table 3-1](#).

Table 3-1 Sensitivity of sample size to different response rates for 148 participants per group (N=444) and treatment differences for level of significance alpha = 0.05

HCQ/HCQ plus AZ Response Rate (%)	Standard of care response rate	Odds Ratio	Treatment difference (%)	Power (%)
50	35	1.86	15	74
50	30	2.33	20	94
50	25	3.00	25	99
60	45	1.83	15	73
60	40	2.25	20	93
60	35	2.79	25	99
70	55	1.91	15	76
70	50	2.33	20	94
70	45	2.85	25	99

3.2 Secondary endpoint

Data available from recent studies published by [Gautret et al., 2020](#) would indicate that viral clearance for hydroxychloroquine plus azithromycin is high. In one study, all participants receiving this combination therapy achieved viral clearance by Day 6. Participants receiving standard of care generally do not achieve a response rate higher than 50%. However, many of these studies are small and often not randomized. If one were to assume that hydroxychloroquine plus azithromycin has an 80% response rate by Day 15 and standard of care has a 50% response rate by Day 15, under this scenario, using the sample size justified for the primary efficacy endpoint, the 30% treatment difference corresponds to an odds-ratio of 4.0 and given 148 participants per treatment group. There will be more than 99% power to detect such a treatment difference.

4 Change to protocol specified analyses

None.

5 Appendix

5.1 Imputation rules

5.1.1 Study drug

Not applicable.

5.1.2 AE date imputation

Partial AE start and end dates will be imputed. If there is uncertainty whether an AE occurred treatment-emergent or not, imputation will be performed, such that AE will be considered as treatment-emergent. Rules for imputing AE end date or start date will be provided in Programming Dataset Specification (PDS) document in details.

5.1.3 Concomitant medication date imputation

Rules for imputing the CM end date or start date will be provided in Programming Dataset Specification (PDS) document in details.

5.1.4 Concomitant therapies and procedures date imputation

The missing dates will be imputed using the same rule as for the concomitant medication.

5.2 AEs coding/grading

The verbatim term recorded on CRF will be identified as adverse event and will be coded by primary system organ class and preferred term using Medical Dictionary for Regulatory Activities (MedDRA) version 23.0 and above.

5.3 Safety derivations

5.3.1 Laboratory parameters derivations

CTCAE grade for the laboratory parameters assess in the trial are provided in [Table 5-1](#).

Table 5-1 CTCAE grades for laboratory parameters (CTCAE Version 5.0)

		Grade			
Abnormality	Lab parameter	1	2	3	4
Hematology					
Anemia	Hemoglobin (g/L)	<LLN - 100 g/L	<100 - 80 g/L	<80 g/L; transfusion indicated	Life-threatening consequences; urgent intervention indicated
Platelet count decreased	Platelets (thrombocytes) (10 ⁹ /L)	<LLN-75.0 x 10 ⁹ /L	<75.0 - 50.0 x 10 ⁹ /L	<50.0 - 25.0 x 10 ⁹ /L	<25.0 x 10 ⁹ /L
White blood cell decreased	Leukocytes (WBCs) (10 ⁹ /L)	<LLN - 3.0 x 10 ⁹ /L	<3.0 - 2.0 x10 ⁹ /L	<2.0 - 1.0 x 10 ⁹ /L	<1.0 x 10 ⁹ /L
Neutrophil count decreased	Absolute neutrophil count (10 ⁹ /L)	<LLN - 1.5 x10 ⁹ /L	<1.5 - 1.0 x10 ⁹ /L	<1.0 - 0.5 x10 ⁹ /L	<0.5 x10 ⁹ /L

		Grade			
Abnormality	Lab parameter	1	2	3	4
Lymphocyte count decreased	Absolute lymphocyte count (10 ⁹ /L)	<LLN x 0.8 - 10 ⁹ /L	<0.8 - 0.5 x 10 ⁹ /L	<0.5 - 0.2 x 10 ⁹ /L	<0.2 x 10 ⁹ /L
Lymphocyte count increased	Absolute lymphocyte count (10 ⁹ /L)		>4 – 20 x 10 ⁹ /L	> 20 x 10 ⁹ /L	
Chemistry					
Liver function					
Alanine aminotransferase increased	ALT (SGPT) (U/L)	ULN - 3.0 x ULN if baseline was normal; 1.5 - 3.0 x baseline if baseline was abnormal	>3.0 - 5.0 x ULN if baseline was normal; >3.0 - 5.0 x baseline if baseline was abnormal	>5.0 - 20.0 x ULN if baseline was normal; >5.0 - 20.0 x baseline if baseline was abnormal	>20.0 x ULN if baseline was normal; >20.0 x baseline if baseline was abnormal
Aspartate aminotransferase increased	AST (SGOT) (U/L)	>ULN - 3.0 x ULN if baseline was normal; 1.5 - 3.0 x baseline if baseline was abnormal	>3.0 - 5.0 x ULN if baseline was normal; >3.0 - 5.0 x baseline if baseline was abnormal	>5.0 - 20.0 x ULN if baseline was normal; >5.0 - 20.0 x baseline if baseline was abnormal	>20.0 x ULN if baseline was normal; >20.0 x baseline if baseline was abnormal
Blood bilirubin increased	Bilirubin (µmol/L)	>ULN - 1.5 x ULN if baseline was normal; > 1.0 - 1.5 x baseline if baseline was abnormal	>1.5 - 3.0 x ULN if baseline was normal; >1.5 - 3.0 x baseline if baseline was abnormal	>3.0 - 10.0 x ULN if baseline was normal; >3.0 - 10.0 x baseline if baseline was abnormal	>10.0 x ULN if baseline was normal; >10.0 x baseline if baseline was abnormal
GGT increased	Gamma-glutamyl transferase (GGT) (U/L)	>ULN - 2.5 x ULN if baseline was normal; 2.0 - 2.5 x baseline if baseline was abnormal	>2.5 - 5.0 x ULN if baseline was normal; >2.5 - 5.0 x baseline if baseline was abnormal	>5.0 - 20.0 x ULN if baseline was normal; >5.0 - 20.0 x baseline if baseline was abnormal	>20.0 x ULN if baseline was normal; >20.0 x baseline if baseline was abnormal
Alkaline phosphatase increased	Alkaline Phosphatase (U/L)	>ULN - 2.5 x ULN if baseline was normal; 2.0 - 2.5 x baseline if baseline was abnormal	>2.5 - 5.0 x ULN if baseline was normal; >2.5 - 5.0 x baseline if baseline was abnormal	>5.0 - 20.0 x ULN if baseline was normal; >5.0 - 20.0 x baseline if baseline was abnormal	>20.0 x ULN if baseline was normal; >20.0 x baseline if baseline was abnormal
Electrolytes					
Hypermagnesemia	Magnesium (Mg)	>ULN - 1.23 mmol/L	-	>1.23 - 3.30 mmol/L	>3.30 mmol/L; life-threatening consequences
Hypomagnesemia	Magnesium (Mg)	<LLN - 0.5 mmol/L	<0.5 - 0.4 mmol/L	<0.4 - 0.3 mmol/L	<0.3 mmol/L; life-threatening consequences
Hypokalemia	Potassium (K)	<LLN - 3.0 mmol/L	Symptomatic with <LLN - 3.0 mmol/L; intervention indicated	<3.0 - 2.5 mmol/L; hospitalization indicated	<2.5 mmol/L; life-threatening consequences

Abnormality	Lab parameter	Grade			
		1	2	3	4
Hyperkalemia	Potassium (K)	>ULN - 5.5 mmol/L	>5.5 - 6.0 mmol/L; intervention initiated	>6.0 - 7.0 mmol/L; hospitalization indicated	>7.0 mmol/L; life-threatening consequences
Cardiac abnormalities					
Renal function Note: A semi-colon (;) indicates 'or' within the description of the grade.					
CPK increased	CPK (creatinine phosphokinase)	>ULN - 2.5 x ULN	>2.5 x ULN - 5 x ULN	>5 x ULN - 10 x ULN	>10 x ULN
Creatinine increased	Creatinine (µmol/L)	>ULN - 1.5 x ULN	>1.5 - 3.0 x baseline; >1.5 - 3.0x ULN	>3.0 baseline; >3.0 - 6.0 x ULN	>6.0 x ULN
Metabolism					
Hypoglycemia	Glucose (mmol/L)	<LLN - 55 mg/dL; <LLN - 3.0 mmol/L	<55 - 40 mg/dL; <3.0 - 2.2 mmol/L	<40 - 30 mg/dL; <2.2 - 1.7 mmol/L	<30 mg/dL; <1.7 mmol/L; life-threatening consequences; seizures

Note: summary statistics for laboratory parameters will only be based on laboratory measurements. Therefore the definition of CTCAE grade in these summary may slightly differ from the above definition.

